**Please note:**

We have increased the total N from 445 to 650, an increase of about 200. This was done for 2 reasons:

1. We previously added a sub study in a prior modification and did not increase the N at that time because enrollment numbers were lower. We have since then consented several individuals to the sub study and we are close to reaching our current N.

2. In the beginning, most individuals we consented for the main smoking study were eligible, however, after consenting approximately 200 individuals, we are having more difficulty consenting individuals who meet eligibility after screening. We may Consent 5 individuals and only 1 is eligible.

We are still keeping the main study at 300 individuals, therefore we are not updating the total N in the consent form. We may need to consent 400 people in order to have 300 eligible.

**2 \* Provide the plan for data analysis. Include in the description the types of comparisons that are planned (e.g., comparison of means, comparison of proportions, regressions, analysis of variance, etc.), which is the primary comparison/analysis, and how the analyses proposed will relate to the primary purposes of the study:**

**Primary Aims:** We will use generalized linear mixed models (SAS, 9.3: Proc GLIMMIX) using a contrast for each post baseline time point to assess the main effects of bupropion vs. placebo (Drug) and PSF vs. SOC (Beh) on smoking cessation. In addition we will assess the interaction of Drug\*Beh and any covariates that were identified above. The test of the hypotheses will be the test of whether the coefficients for the main effects and the interaction are significantly different from 0 based on the likelihood ratio test. If the interaction is significant, we will run additional analyses to explore the simple main effects and will interpret those as opposed to the main effects.

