**Exploratory Analyses:**

**Other smoking outcomes:** We will use a Generalized Linear Mixed Model (GLMM; Proc MIXED) to assess if the treatment conditions have a significant effect on other smoking outcomes (e.g. number of cigarettes smoked per day) over time. Treatment conditions, time and the interaction of time with the treatment conditions will be included in the model. A random intercept will be used to account for the non-independence of the repeated measures. An unstructured covariance matrix will be employed. Significant effects will be followed up with specific contrast statements.

**Mediation:** We will use Proc Mixed to assess the interventions impact on possible mediating variables for bupropion (craving, withdrawal) and for PSF (self-efficacy, depression, loneliness, substance abuse). Mediators will be assessed at 12 weeks, controlling for baseline. For those variables that are significant we will conduct additional analyses to determine if change in those mediators is related to smoking cessation at 24 weeks. If all conditions are met, we will use the MacKinnon 121 approach to formally assess for mediation of smoking cessation by the targets of the interventions.

**Moderators:** We will assess possible clinical (e.g. depression, smoking severity at baseline, years smoked) and demographic (e.g. age, race) moderators on smoking cessation. We use the analyses described in For Aims 1-3 to assess moderation by including these variables and their interaction with the treatment conditions to the models.

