Exploratory Analyses: Other smoking outcomes: We will use a Generalized Linear Mixed Model (GLMM; Proc MIXED) to assess if the treatment conditions have a significant effect on other smoking outcomes (e.g. number of cigarettes smoked per day) over time. Treatment conditions, time and the interaction of time with the treatment conditions will be included in the model. A random intercept will be used to account for the nonindependence of the repeated measures. An unstructured covariance matrix will be employed. Significant effects will be followed up with specific contrast statements. Mediation: We will use Proc Mixed to assess the interventions impact on possible mediating variables for bupropion (craving, withdrawal) and for PSF (self-efficacy, depression, loneliness, substance abuse, and dosage of the PSF intervention (number of sessions completed)). Mediators will be assessed at 12 weeks, controlling for baseline. For those variables that are significant we will conduct additional analyses to determine if change in those mediators is related to smoking cessation at 36 weeks. If all conditions are met, we will use the MacKinnon 100 approach to formally assess for mediation of smoking cessation by the targets of the interventions. Moderators: We will assess possible clinical (e.g. depression, smoking severity at baseline, years smoked, etc.) and demographic moderators on smoking cessation. We use the analyses described for the primary aim to assess moderation by including these variables and their interaction with the treatment conditions to the models

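### The cigarettes-per-day analysis pairs a generalized linear mixed model with Proc MIXED and does not adjust for baseline cigarettes per day, which under assumed distributions gives up power that costs nothing to recover

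*SAP*

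**What the plan says.** The SAP, under Exploratory Analyses (Other smoking outcomes), plans a "Generalized Linear Mixed Model (GLMM; Proc MIXED) to assess if the treatment conditions have a significant effect on other smoking outcomes", and gives as its example "e.g. number of cigarettes smoked per day) over time". On the model terms it says: "Treatment conditions, time and the interaction of time with the treatment conditions will be included in the model". A random intercept is added, and then "An unstructured covariance matrix will be employed". The Protocol (Sample Size and Data Analysis, item 2, Exploratory Analyses) has the same pairing: "We will use a Generalized Linear Mixed Model (GLMM; Proc MIXED".

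Neither document gives a distribution, link or transformation for this outcome, and neither says whether baseline is a response or a covariate. Two contrasts within the plan are relevant:

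- For abstinence, the Protocol's Primary Aims text pairs the generalized class with a different procedure: "We will use generalized linear mixed models (SAS, 9.3: Proc GLIMMIX) using a contrast for each post baseline time point".
- The mediator models, described directly after this one, are adjusted for baseline; this one is not. Under Covariate Selection, extra covariates enter when they are significantly out of balance, so baseline smoking would come in only by that route.

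**The concern.** There are two separate problems.

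First, the label and the procedure conflict. An analyst told to fit a generalized linear mixed model in Proc MIXED must either fit a normal model and ignore the label, or change procedure and ignore the instruction. Cigarettes per day after a quit attempt is a skewed count with a cluster of zeros, so the choice affects the analysis and should be made before data are seen.

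Second, and more important for power, baseline smoking is not used as a covariate. It is likely to be among the strongest predictors of later smoking and is already scheduled for collection. What is at stake is the trial's ability to detect a reduction in consumption, which is what this outcome adds to abstinence, and whether the reported mean difference is driven by a few heavy smokers.

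**Working it through.** **Inputs from the documents.** 300 randomised less 20% attrition: 300 × 0.80 = 240, or 60 per cell and 120 per level of each factor (SAP, Power Calculations). Visits are at baseline, week 12 and week 36. Abstinence is 10% v 25% for bupropion (Protocol, Sample Size and Data Analysis, item 1). The plan states no mean, SD, effect or power for cigarettes per day, so there is no planned figure to reproduce.

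**Assumptions, not from the documents.** Baseline mean 5 to 15 per day; between-person SD of log cigarettes 0.4 to 1.0; negative binomial counts around each person's mean; quitters at zero; continuing control smokers at 80% of baseline. The active arm has either the quitting effect alone or a further 15% relative reduction among continuing smokers.

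At a baseline mean of 10, the follow-up means are:

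- control: 0.90 × 0.80 × 10 = 7.2
- active, quitting only: 0.75 × 0.80 × 10 = 6.0 (difference 1.2)
- active, with the further reduction: 0.75 × 0.80 × 0.85 × 10 = 5.1 (difference 2.1)

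**Why the change contrast loses power.** With complete data and an unstructured covariance, a treatment-by-time contrast with baseline as a response reduces to a difference in mean change. Let s0 and s1 be the baseline and follow-up SDs, ρ their correlation, and b = ρ·s1/s0 the slope of follow-up on baseline.

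- Variance of change: s0² + s1² − 2ρ·s0·s1
- Residual variance with baseline as a covariate: s1²(1 − ρ²)
- Difference: (s0 − ρ·s1)² = s0²(1 − b)²

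The change contrast is therefore never better, and the two are equal only when b = 1. Under the assumptions, control follow-up is 0.90 × 0.80 = 0.72 of a person's own mean, so b is at most 0.72 in that arm. It is lower still because one visit's count measures that mean with error. The excess variance is at least (1 − 0.72)² = 0.078 of the baseline variance.

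**Simulated power, 120 v 120, two-sided 5%, range across settings**

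| Assumed effect | Raw change | Baseline as covariate (normal model) | Gain |
|---|---|---|---|
| Quitting only | 17–26% | 25–42% | roughly 8–16 points |
| Plus 15% further reduction | 37–66% | 63–91% | roughly 25–30 points |

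Null rejection was about 4 to 7.5%. With some 500 trials per setting, each power figure has a simulation error of about 2 points, so the ends of these ranges are approximate.

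**What a count model adds.** Relative to the baseline-adjusted normal model, a negative binomial log-link model with log baseline as covariate adds little at log-SD 0.4 and about 2 to 13 points at log-SD 1.0. Other runs under the same assumptions put the upper end as high as 18 points. A Poisson random-intercept model is not a safe substitute: under the null it rejected 6.7 to 32.3% of the time in a separate set of simulations with overdispersed counts.

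**Covariance.** An unstructured matrix over three visits already has 3 × 4/2 = 6 free parameters and is saturated. A random intercept adds a seventh that cannot be separately identified.

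**The case against.** The plan does not say that baseline is a response. The primary models use post-baseline time points, and both documents promise to inspect distributions before modelling, so a transformation is not ruled out. This stands: the change-score reading is an inference, and the gains above are conditional on it. It does not remove the point. If only weeks 12 and 36 are responses and there is no baseline covariate, the residual variance is s1² instead of s1²(1 − ρ²), so baseline information is still unused. The interaction would then test only whether the effect differs between those two visits.

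A reader might infer that the text names a log-link count model and that Proc MIXED forfeits a known amount of power against it. The documents do not support this. They name only a model class, which includes the normal identity-link case; no log link or count distribution is mentioned. Most of the loss comes from the handling of baseline, not from the procedure. In one set of simulations a negative binomial mixed model without baseline adjustment ranged from 18.5 points below to 21.8 points above a normal model with it.

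The sizes also depend on assumptions. Proportional effects favour a log link, and the further 15% reduction appears nowhere in the documents. Finally, the outcome is an example under Exploratory Analyses with no power claim attached.

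**Conclusion.** The point holds in a limited form. The mismatch between model and procedure is in the text of both documents, and the stated model does not adjust for baseline cigarettes per day. On the natural reading, adding baseline as a covariate gains roughly 8 to 16 points of power for a quitting effect alone and roughly 25 to 30 points with the assumed further reduction. These figures rest on the assumed means, spreads and effects listed above and are not properties of the plan. The benefit of a count model beyond that is small at modest spread and moderate at wide spread.

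A reader might also fear false positives. The simulations do not show that: the raw-change contrast rejected close to the nominal 5% under the null. The primary abstinence analysis is not affected. This is a worthwhile correction to an exploratory analysis, not a threat to the trial's main conclusion.

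**What to change.** In both documents, replace the sentences on other smoking outcomes so that they state the following:

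1. **Outcomes and baseline.** Weeks 12 and 36 are the responses, and baseline cigarettes per day is a covariate whether or not it is out of balance.
2. **Model and procedure, one of two.** Either a linear mixed model, so named, in Proc MIXED with empirical standard errors; or a negative binomial log-link model in Proc GLIMMIX with log baseline as covariate, reporting rate ratios.
3. **Zero baselines, if the log is used.** Give a rule. The recruitment advertisement admits people who smoked at least one cigarette in the last week, so a daily figure can fall below 1 and be recorded as zero.
4. **Covariance.** Use either the random intercept or the unstructured residual matrix, not both.

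The cost is a few sentences and a small change of code, with no new data, since the baseline assessment is already scheduled. If the count model is chosen, there is one small downside: results are rate ratios rather than mean differences in cigarettes.

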We propose to randomize 300 participants to one of the following 4 conditions: (1) bupropion + Positively Smoke Free (an 8 session tailored behavioral intervention for PLWH smokers); (2) bupropion + Standard of Care (brief advice to quit); (3) Placebo + Positively Smoke Free; and (4) Placebo + Standard of Care. Given the factorial nature of the design, we will be able to assess the main effect of bupropion vs. Placebo, Positively Smoke Free vs. Standard of Care, and the additive effect of those two treatments. We chose to use a factorial design as it is a highly efficient method of assessing multiple treatments in a single trial with the possibility of saving both time and resources. All participants will be assessed at baseline, 12 weeks and 36 weeks (6 months post study completion).

Participants will be randomly assigned to one of the four conditions using permuted blocks which will randomly vary in size. The research pharmacy will be notified of the drug randomization (bupropion or placebo). All raters, investigators, and other staff will be blind to treatment assignment except for the dispensing pharmacist.

Separate emergency unblinding envelopes for each participant will be kept in a locked cabinet at the dispensing pharmacy in the case of a medical emergency. All participants who are randomized will be taught the correct use of the study medication, and assisted in setting a quit date.

Sub study:

There will be no group assignment or randomization.

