PSF is an intensive, tailored, social cognitive theory-driven intervention that promotes cessation in PLWH smokers. Its development was guided by previous pilot work characterizing the sociobehavioral drivers of tobacco use in PLWH 40. It is an 8-session program, with session lengths ranging from 45-60 minutes. A syllabus serves as a guide for therapists. The course content has gone through multiple rounds of revision in response to input from intra and extra-institutional experts in HIV and smoking cessation, PLWH smokers, and the ID Clinic community advisory board. Themes of particular relevance to HIV-infected smokers permeate the course content, and the heterogeneity of the PLWH community and how this relates to smoking behaviors (i.e. similarities and differences between drug users, LGBT, and depressed individuals) is highlighted. The "microtargeting" of these subsets of PLWH has received the praise of group participants. An overview of the course content, including tailoring themes, has been previously published. All treatment sessions are audiotaped. If a participant misses an intervention session, we will call him/her to reschedule. If the participant is having difficulty attending some of the sessions in person, we will offer to conduct them over the telephone.

Control Condition

Those randomized to standard of care will receive of standard of care smoking cessation treatment by a trained research assistant at the time of randomization. Participants will be given a quit smoking brochure and brief advice to quit (i.e. < five minutes)

Follow Up Assessment Interviews:

All participants will be re-assessed at approximately week 12 and approximately week 36. Vital signs will also be recorded. All assessments will be administered in a confidential and private location by experienced research assistants who are masked to the results of randomization. The list of assessments to be completed are located in the study schedule in the Additional Documents section.

Participants will also complete a brief visit when they return at week 1, 2, 4, and 8 for their medication refill. All participants will complete vital signs as well as answer a few questions about their medication side effects (if any), medication adherence, their mood and smoking status.

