**Expired carbon monoxide (CO):**

Expired air CO provides an accurate indirect measure of carboxyhemoglobin (COHb) level and is a standard biochemical method for assessing a smoker's level of intake. According to the SRNT Subcommittee on Biochemical Classification report, measuring CO provides a sensitivity and specificity of approximately 90% for current tobacco use. Expired air CO will be assessed with using a Smokerlyzer-Breath Carbon Monoxide Monitor.

Expired CO will be monitored at each visit (Screening, Evaluation Phase, Baseline, week 1, 2, 4, 8, 12, and week 36).

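### Number of PSF sessions is not a valid mediator of PSF versus SOC under the SAP's procedure; separately, the protocol's week-24 mediation outcome has no visit and conflicts with the SAP's week 36.

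*SAP*

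**What the plan says.** The SAP (Exploratory Analyses, Mediation) names two mediators for bupropion, craving and withdrawal. It names five for PSF: self-efficacy, depression, loneliness, substance abuse and "dosage of the PSF intervention (number of sessions completed". All seven go through one sequence.

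- First, the effect of treatment on the mediator: "Mediators will be assessed at 12 weeks, controlling for baseline".
- Second, for mediators that pass, further analyses to "determine if change in those mediators is related to smoking cessation at 36 weeks".
- Third, if every condition is met, a formal mediation test.

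The SAP does not say whether treatment arm is a term in the second-step model.

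The protocol (Sample Size and Data Analysis, item 2, Mediation) has the same paragraph with two differences. Its PSF list stops at four, "for PSF (self-efficacy, depression, loneliness, substance abuse", so session count is absent. Its second step is to "determine if change in those mediators is related to smoking cessation at 24 weeks".

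On timing, the protocol (Study Procedures, Follow Up Assessment Interviews) says "All participants will be re-assessed at approximately week 12 and approximately week 36". Its carbon monoxide section says "Expired CO will be monitored at each visit (Screening, Evaluation Phase, Baseline, week 1, 2, 4, 8, 12, and week 36".

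**The concern.** A mediator analysed this way needs a value before treatment and must be able to vary in both arms. Session count does neither. PSF appointments are arranged only after randomisation, so nobody has a baseline count. SOC participants receive a brochure and a few minutes of advice, so their count is zero by design. A treatment effect on this mediator says only that PSF was offered to one group and not to the other.

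What remains is whether people who attended more sessions quit more often. Attendance is chosen by the participant, and motivated smokers may both attend and quit. An association of that kind could be reported as PSF working through dose.

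Separately, the protocol ties the mediation outcome to a week at which CO-verified abstinence cannot be obtained, because no visit takes place then.

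**Working it through.** The documents give no figure for the mediation analysis, so there is none to reproduce. The sample size behind it does reproduce: 300 × 0.80 / 4 = 60 per cell, hence 120 PSF and 120 SOC, as the SAP states.

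**Inputs from the documents.** 120 per arm (SAP, Power Calculations); 8 PSF sessions and none in SOC (Protocol, Study Procedures); abstinence of 7% with SOC and 20% with PSF (Protocol, Sample Size and Data Analysis, item 1). The protocol gives those rates for PSF without drug; using them for the whole arms is a simplification.

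**Assumptions.** The documents give no attendance figures. Means of 3 to 6 sessions with SDs of 2 to 2.5 are assumed for the formulas, and binomial attendance with means of 1 to 6 for the simulations.

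**Step 1, treatment to mediator.** With SOC fixed at zero, t = mean / (SD / √120).

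- Mean 3, SD 2.5: 3 / (2.5 / 10.95) = 13.1
- Mean 5, SD 2.5: 21.9
- Mean 6, SD 2: 32.9

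The effect of PSF on smoking does not enter this formula. In 2,000 simulated trials at each mean of 1, 2, 4 and 6 sessions, the step was significant every time; the smallest t, at a mean of 1, was 8.5.

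**Baseline term.** If everyone's baseline count is set to zero, that column is constant and the design matrix (intercept, arm, baseline) has rank 2 of 3. The baseline coefficient cannot be estimated, and change is simply attendance.

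**Step 2, mediator to cessation, arm included.** All SOC counts are zero, so SOC fixes only the intercept and the arm term absorbs the rest. In one simulated data set the session coefficient was 0.0299 (SE 0.140) in the full model and the same in a PSF-only model. With shared covariates the identity need not be exact, but SOC still contributes no variation in sessions.

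Arm and sessions are also strongly correlated: r² = 0.25m² / (0.25m² + 0.5SD²).

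- m = 3, SD = 2.5: 2.25 / (2.25 + 3.125) = 0.42, so r = 0.65 and variance inflation 1/(1 − r²) = 1.7
- m = 6, SD = 2: 9 / (9 + 2) = 0.82, so r = 0.90 and variance inflation 5.5

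**Step 2, arm in or out.** Taking no dose effect within PSF, rates of 20% and 7%, and mean attendance of 4, the session term was significant in 75% of 2,000 simulated trials without arm and in 4.5% with it. Without arm, session count stands in for arm. The 75% belongs to that attendance pattern; more scattered attendance makes a weaker proxy and lowers it.

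**Self-selection with arm included.** If motivation alone produced an odds ratio of 1.25 per SD of sessions within PSF, the step would be significant in roughly 13 to 16% of trials; at 1.5, roughly 34 to 42%; at 2.0, roughly 76 to 86%. Adjusting for arm does not remove this.

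**Timing.** Post-baseline visits are at weeks 1, 2, 4, 8, 12 and 36. Week 24 is not among them. The SAP's week 36 is.

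**The case against.** A reader might infer that the mediation analysis cannot be run at all. The documents do not support that. Six of the seven SAP mediators are untouched by the session-count problem and fit a week-12, baseline-adjusted, week-36 sequence. Even for session count, software would drop the constant baseline term and return estimates. The fault lies in what those estimates mean.

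A reader might also infer that the plan would almost certainly declare sessions a significant mediator. That is true of the first step only. The sequence has two further conditions, and the second depends on whether arm is in the model and on how strong self-selection is, neither of which the documents settle.

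A third tempting claim is that sessions are not on the pathway from treatment at all. Under intent-to-treat the randomised variable is assignment, and sessions attended do follow from it. The objection that stands is narrower: the association is identified only within PSF and is confounded by whatever drives attendance.

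The two defects also sit in different documents. Session count is only in the SAP; week 24 is only in the protocol. The protocol's figure may mean 24 weeks after the 12-week treatment period, since 36 − 12 = 24 and its design section says "All participants will be assessed at baseline, 12 weeks and 36 weeks (6 months post study completion". Its mediation paragraph does not say so.

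Finally, the analysis is labelled exploratory, and no primary or secondary aim depends on it. All of these points stand. None of them makes session count interpretable under the stated procedure.

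**Conclusion.** Wrong as written, and of low severity. The SAP's procedure cannot show that session count mediates PSF versus SOC. The first step is passed by construction. The second is either driven by the arm difference or identified only from self-selected attendance within PSF. The zero in SOC and the missing baseline follow from the design and need no assumption. The sizes (t of 13 to 33, and 75% against 4.5%) rest on assumed attendance and on the protocol's planning rates.

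The damage is confined to one of seven exploratory mediators. The primary comparisons are unaffected.

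The protocol's week 24 is a separate inconsistency with the visit schedule and with the SAP.

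**What to change.** - **SAP, Mediation:** remove number of sessions from the mediator list.
- **Attendance:** report it as an exploratory dose-response within the PSF arms (about 120 participants expected), adjusted for readiness to quit before randomisation and described as non-causal. The protocol already collects the Readiness to Quit Ladder at screening. A complier-type estimate with randomised arm as the instrument is optional; it would need the stated assumption that assignment affects cessation only through sessions attended.
- **Remaining six mediators:** state that treatment arm is a term in every mediator-to-outcome model.
- **Protocol, Mediation:** reconcile the 24-week outcome with the SAP's week 36, which is a scheduled visit.

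The cost is a few sentences in the SAP and one in the protocol. It needs no new data, visits or participants.

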Female participants who have the potential to become pregnant will have a pregnancy test during the evaluation phase and approximately monthly during the study (while taking study medication). They will be asked to use acceptable method of contraception during the medication phase of the study (week 1-12). Participants will sign a contraception consent to confirm their agreement (In the baseline packet). Condoms will also be provided at research appointments.

Baseline Interview:

Participants will also complete a series of assessment questionnaires (baseline interview). Vital signs will also be recorded. Only those continuing to meet full inclusion criteria and do not meet exclusion criteria will proceed to randomization and remain in the study. The list of assessments to be completed are located in the study schedule in the Additional Documents section.

Randomization

Study participants who are deemed eligible for the study will complete baseline testing and will then be randomized 1:1:1:1 to four study conditions: (1) Bupropion + PSF; (2) Bupropion + SOC; (3) Placebo + PSF; (4) Placebo + SOC. Participants will be randomly assigned to one of the four conditions using permuted blocks which will randomly vary in size. The research pharmacy will be notified of the drug randomization (Bupropion or placebo). All raters, investigators, and other staff will be blind to treatment assignment except for the dispensing pharmacist. Separate emergency unblinding envelopes for each participant will be kept in a locked cabinet at the dispensing pharmacy in the case of a medical emergency. All participants who are randomized will be taught the correct use of the study medication, and assisted in setting a quit date with the instruction to quit on approximately Day 8 (beginning of Week 2) following one week of medication.

Medication Intervention:

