Covariate Selection: We expect, due to randomization and sufficiently large sample size, that demographic, clinical characteristic, and outcome variables at baseline in the four conditions will not be significantly different. However, we will perform tests for differences (imbalances) on demographic (e.g. age, race, gender) and other potential confounder variables across the four groups. Imbalances may occur in spite of the randomization procedure. If there are important variables significantly out of balance we will add them as covariates in the models. In addition, all models will include covariates indicating whether the participants are using HAART.

Missing Data: Missing data can arise from active refusal and from participants who cannot be located. Attrition will be carefully monitored. We will attempt to assess all participants at follow up regardless of whether they engage with smoking cessation services during the study (intent-to-treat). To assess the potential confounding effects of missing data, we will compare the baseline characteristics of participants who do and do not complete the 12- and 36-week assessments. If we find significant differences between dropouts and completers and differential attrition, we will include any potential confounding variables as covariates. If a subject fails to complete interim visits, we will attempt to re-engage him/her for the 36 week visit in order to ascertain the primary abstinence endpoint. If a subject refuses to be contacted or otherwise loses contact with the investigators, we will censor data at the point of loss and the subject will be considered non-abstinent. In addition, the investigative team will agree by consensus on a set of rules to guide the imputation of missing data.

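### The exploratory mediation analysis does not separate week-12 mediator change from abstinence already reached by week 12, so a consequence of quitting can be declared a mediator

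*SAP*

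**What the plan says.** The protocol (Study Procedures, Randomization) instructs participants to "quit on approximately Day 8 (beginning of Week 2) following one week of medication".

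The mediation paragraphs are in the protocol (Sample Size and Data Analysis, item 2, Exploratory Analyses) and the SAP (Exploratory Analyses). Both list craving and withdrawal for bupropion, and self-efficacy, depression, loneliness and substance abuse for PSF. The SAP adds the number of PSF sessions completed. The steps are:

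1. Test whether treatment affects the mediator: "Mediators will be assessed at 12 weeks, controlling for baseline".
2. For mediators that pass, "determine if change in those mediators is related to smoking cessation at 36 weeks" (SAP). The protocol instead has "determine if change in those mediators is related to smoking cessation at 24 weeks".
3. If all conditions are met, apply the MacKinnon approach.

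On covariates, the SAP says "all models will include covariates indicating whether the participants are using HAART". It also adds variables found to be imbalanced or related to attrition. Neither document mentions week-12 abstinence, time order or a sensitivity analysis for mediation.

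The protocol schedules CO at every visit, including weeks 1, 2, 4, 8, 12 and 36. Brief questions on mood and smoking status are asked at weeks 1, 2, 4 and 8 (Follow Up Assessment Interviews).

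**The concern.** Day 8 to week 12 (day 84) is 76 days, or about 11 weeks. A participant's week-12 mediator value may therefore be a result of having quit or not. Smoking status at week 12 can also be expected to predict status at week 36. A variable that merely follows from quitting would then differ by arm, because more treated participants have quit. It would also predict week-36 abstinence, because quitters tend to stay quit. It would pass both screening steps without being a cause of anything.

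The documents make the reverse path plausible. Research Related Risks lists depressed mood and withdrawal among the common effects of stopping, though it calls them short-lived, so their size at week 12 is uncertain. The background section says PSF aims to raise abstinence self-efficacy, so a direct treatment effect on that mediator is part of the trial's own rationale.

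At stake is a claim about mechanism. The report could say that PSF works through self-efficacy when the data show only that people who had quit feel more confident and tend to stay quit.

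**Working it through.** **The plan's own figures.** The documents give no operating figure for the mediation analysis. The sample size reproduces: 300 × 0.8 = 240, which is 60 per cell and 120 per main-effect arm. Power at 120 per arm, two-sided 0.05, is 87% for 10% v 25% and 84% for 7% v 20%, consistent with the protocol's figure of over 80%.

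**Inputs.** From the documents: 120 per arm, mediator at week 12 adjusted for baseline, outcome at week 36. Assumed, because the documents are silent:
- week-12 abstinence 15% v 30%;
- week-36 abstinence 55% if abstinent at week 12 and 5% if not, which implies 0.15 × 0.55 + 0.85 × 0.05 = 12.5% v 0.30 × 0.55 + 0.70 × 0.05 = 20% at week 36;
- baseline to week-12 mediator correlation 0.5;
- quitting shifts the mediator by d = 0.5, 0.8 or 1.0 SD;
- the mediator has **no** effect on week-36 abstinence.

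**Step 1, by hand.** The arm difference produced through quitting alone is d × (0.30 − 0.15), that is 0.075, 0.12 and 0.15 SD. The standard error is about √0.75 × √(2/120) = 0.112. The ratios are 0.67, 1.07 and 1.34, so step 1 is seldom passed. A direct effect of 0.4 SD raises the differences to 0.475, 0.52 and 0.55 SD and the ratios to 4.2, 4.7 and 4.9, so step 1 is almost always passed. The direct effect therefore drives the result.

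**Simulation.** Step 1 is a linear model of the week-12 mediator on treatment and baseline. Step 2 is a logistic model of week-36 abstinence on treatment, baseline and week-12 mediator. A Sobel test stands in for the MacKinnon step. False declarations of mediation:

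| Shift from quitting | Through quitting only: steps 1 and 2 | with Sobel | Plus 0.4 SD direct: steps 1 and 2 | with Sobel |
|---|---|---|---|---|
| 0.5 SD | 5% | 1% | 52% | 39% |
| 0.8 SD | 15% | 5% | 85% | 78% |
| 1.0 SD | 23% | 9% | 95% | 89% |

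Repeat runs agree within about three percentage points. A direct effect of 0.2 SD gives 35%, 66% and 78% for steps 1 and 2. If quitting does not shift the mediator, the rate is at most about 5% in every setting.

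**Other abstinence rates.** Week-12 rates of 15% v 40%, with 60% and 2% abstinent at week 36, imply 0.15 × 0.60 + 0.85 × 0.02 = 10.7% v 0.40 × 0.60 + 0.60 × 0.02 = 25.2% at week 36, close to the plan's bupropion effect. The two-step rates with no direct effect are then 13% (0.5 SD) and 50% (1.0 SD). With a 0.3 SD direct effect they are about 67% and 99%. Week-12 rates of 7% v 20%, with 60% and 3%, give 4% and 16% with no direct effect.

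**Effect of adjusting.** Adding week-12 abstinence to step 2 brings false declarations to about 5% or less. The opposite case was also simulated: treatment truly changes the mediator early, that change produces quitting by week 12, and quitting persists (60% and 3%; week-12 abstinence from 11% v 16% to 14% v 26%). Detection of this genuine mediation falls from 34-71% to 4-6% on adjustment.

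**The case against.** **Nothing in the documents fixes the size.** This stands. A reader might infer that the analysis will report mediation that does not exist. The documents do not support that: the rate runs from under 1% to about 99%, depending on how strongly quitting shifts each mediator and whether treatment also moves it directly. Neither quantity is given. The high rates need the direct effect.

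**The plan does not rule out adjustment.** This stands in part. The phrase about controlling for baseline describes the mediator step. The outcome step is described only as additional analyses, and HAART use enters all models. The defect is that the model is unspecified and no step deals with week-12 abstinence, not that adjustment is excluded.

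**Later steps filter false findings.** They do so in part. The Sobel stand-in lowers the rates but leaves 39-89% when there is a direct effect. The SAP's false discovery rate procedure was not simulated. It may lower the rates further, though the SAP does not say whether it covers exploratory tests, and it does not address the direction of effect.

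**Adjustment can do harm.** This stands and shapes the fix. A cessation treatment may work by changing the mediator, which produces quitting by week 12, which then persists. Week-12 abstinence is then on the causal path. A reader might conclude that only an adjusted effect counts as mediation. That rule would discard most genuine mediation of this kind.

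**It does not fit every listed mediator.** This stands for PSF session count, which has no baseline value and no counterpart under standard of care.

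**Conclusion.** The point holds as a specification gap in an exploratory analysis. For craving, withdrawal, self-efficacy, depression, loneliness and substance abuse, the planned steps cannot tell a cause of abstinence from a consequence of it.

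Under the main assumptions, the two screening steps are falsely passed in about 5-23% of trials if treatment reaches the mediator only through quitting, and in about 50-95% with a further 0.4 SD direct effect. A Sobel-type test lowers these to about 1-9% and 39-89%. The persistence of abstinence and both mediator shifts are assumed, so these figures show a possible range and do not predict a rate for this trial. No primary or secondary aim depends on this analysis. The case for acting is that the remedy is cheap and prevents an unsupported claim about mechanism.

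**What to change.** In the SAP (Exploratory Analyses, Mediation) and the matching protocol paragraph:

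1. Write out the mediator-to-outcome model with its covariates.
2. Report the mediator-to-outcome and indirect-effect estimates with and without CO-verified week-12 abstinence as a covariate. Do not make the adjusted result decisive.
3. If the two disagree, state that the direction of effect cannot be determined and describe the result as an association.
4. Where a mediator is already collected at weeks 1 to 8, also analyse it in time order, before the abstinence it is meant to explain. Mood is one example, if the brief questions are a usable measure. The visible text does not show craving, withdrawal, self-efficacy or loneliness being collected at those visits, and the study schedule is a separate attachment.
5. Reconcile the outcome time. The protocol says 24 weeks and the SAP 36, while the described follow-up assessments are at weeks 12 and 36. The protocol may mean 24 weeks after week 12 (12 + 24 = 36), but it does not say so.

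The cost is one covariate, one more reported estimate per mediator and more cautious wording. Items 1 to 3 and 5 need no new data, and item 4 uses only what is already collected. The adjusted estimate leaves out any effect that acted by producing quitting before week 12, which is why both are reported.
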